15.0 DEFINITIONS and ABBREVIATIONS

15.1 Study Definitions

Access Site Hemorrhage: Bleeding from the access site which requires transfusion, hospitalization (either admission or extended stay), or further treatment for management. Hemorrhage, without frank bleeding, needing ≥ 1 unit RBCs will be considered a serious adverse event.

Access Site Infection: Culture-proven wound infection or presumptive treatment with antibiotics for clinically diagnosed wound infection.

Acute Renal Failure: Acute post-operative renal insufficiency resulting in one or more of the following: (a) increase of >1.0 mg/dl in serum creatinine from most recent prior measured level, and current measured absolute value is >2.0 mg/dl; (b) a new requirement for dialysis.

Adverse Device Effect (ADE): An adverse event related to the use of the medical device. This definition includes any event resulting from insufficiencies or inadequacies in the instructions for use or the deployment of the device. This definition includes any event that is a result of a user error.

Note: This definition includes adverse events resulting from insufficient or inadequate Instructions for Use, deployment, implantation, installation, or operation, or any malfunction of the investigational medical device.

Note: This definition includes any event resulting from insufficiencies or inadequacies in the Instructions for Use, deployment of the device or any event that is a result of user error or intentional abnormal use of the investigational medical device.

Adverse Event (AE): An adverse event (AE) is any untoward medical occurrence, unintended disease or injury, or untoward clinical signs (including abnormal laboratory findings) in subjects, users or other persons, whether or not related to the investigational device/procedure.

Air Embolism: An inadvertent introduction of air or gas to the vasculature that requires medical treatment.

Allergic Reaction: An allergic reaction characterized by rash, nausea, vomiting, upper respiratory congestion, urticaria, shortness-of-breath, vasovagal reaction, or general cardiovascular collapse (anaphylaxis).

Amputation (major): Any requirement for amputation above the ankle or higher.

Amputation (minor): Any requirement for amputation below the ankle.

Amputation, Unplanned: An amputation associated with the target limb that occurs between the index procedure and 30 days that was not previously planned as part of the overall treatment strategy.

	No.: CP 64007	REV. D

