Bacteremia: Presence of viable bacteria in the circulating blood. May be associated with clinical signs/symptoms such as fever. Must be confirmed by having one positive blood culture and no subsequent negative cultures.

Bleeding Complication (Major): Bleeding resulting in ≥ 3 g/dl decrease in hemoglobin (if hemoglobin level not available, a decrease in hematocrit of $\geq 10\%$), or necessitating transfusion of >1 unit of PRBC's /whole blood, or necessitates surgery/endoscopic intervention.

	No.: CP 64007	REV. D
	TITLE: Disrupt PAD+ Study	
	CLASS: CLINICAL PROTOCOL	PAGE 44 OF 57

Access site: Bleeding from the arteriotomy site which requires transfusion, hospitalization (either admission or extended stay), or further treatment for management.

Calcification Classification (study eligibility): Calcification must be: 1) on parallel sides of the vessel and 2) extending >50% the length of the lesion if lesion is ≥50mm in length; or extending for minimum of 20mm if lesion is <50mm in length.

Calcification Classification (PARC): Calcification will be assessed by the angiographic core lab according to the Peripheral Academic Research Consortium (PARC) definition (Patel et al., 2015).

PARC Degree of Lesion Calcification

Focal	Degree of lesion calcification
Mild	<180° and greater than one-half of the total lesion length
Moderate	≥180° (both sides of vessel at same location) and less than one-half of the total lesion length
Severe	>180° (both sides of the vessel at the same location) and greater than one-half of the total lesion length

CAPA: Corrective and Preventative Action.

Cardiac Arrhythmia: Electrical disruption of the heart rhythm requiring specific medication, defibrillation, or pacemaker insertion to address condition.

Cardiogenic Shock: Subject presents with SBP <80 mm Hg for more than 30 minutes, unresponsive to fluids, or requiring intravenous vasopressor agent or an intra-aortic balloon pump (IABP).

Cardiovascular Death: All cardiovascular cause mortality.

Cerebral Vascular Accident (CVA): See Stroke.

Closure, Abrupt: Occurrence of new (during the index procedure), persistent slow, reduced, or loss of flow within the target vessel that requires intervention other than the index or adjunct treatment. Abrupt closure may also be referred to as acute occlusion if there is a total loss of flow.

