Fever: A temperature 38°C (>101.4° F) not related to a culture positive infection.

General Discomfort: Physical or psychosocial signs or symptoms commonly associated with hospitalization that are investigated and determined to require minor (i.e., aspirin, non-narcotic medication) or no treatment.

Hematoma: Collection of blood (or its degradation products) which exceeds 5 cm in diameter, requires treatment, or prolongs hospitalization.

	No.: CP 64007	REV. D
	TITLE: Disrupt PAD+ Study	
	CLASS: CLINICAL PROTOCOL	PAGE 47 OF 57

Hemorrhage: Any bleeding which results in a drop in hematocrit from pre-procedure level which is associated with hemodynamic compromise or which results in a hematocrit of $\leq 30\%$, or blood loss that requires transfusion.

Hypertension: Systolic BP >140 mmHg, or diastolic >90 mmHg requiring specific medical therapy.

Iliofemoral DVT: Defined as DVT involvement of the common or external iliac veins or the common femoral vein, with or without distal (e.g., toward foot) DVT involvement, based on duplex ultrasound exam.

Infection, access site: Infection at the vascular access site, documented by lab culture or clinical evidence requiring medical treatment (irrigation, debridement, antibiotics, etc.) to resolve.

Infection, sepsis: Culture-proven infections or presumptive treatment with antibiotics for clinically diagnosed infection.

Infection, systemic: Systemic infection documented by positive lab culture or clinical evidence, requiring medical treatment to treat and resolve.

Intracranial Hemorrhage: Includes all bleeding within the cranium either subarachnoid, intraparenchymal, or intracerebral.

Intravascular Lithotripsy (IVL), formerly known as Intravascular Lithoplasty: Shockwave Medical's proprietary balloon angioplasty catheter including lithotripsy technology that creates pulsatile mechanical energy for disrupting calcified vascular plaque.

Limb Ischemia: Deficient supply of oxygenated blood to the tissues in the limbs that is due to obstruction of the inflow of arterial blood characterized by pain and/or discoloration of the limb.

Lithotripsy: A medical procedure for disrupting calculus in the body.

Luminal Patency: Post-procedure residual stenosis $<50\%$ as determined by investigator visual assessment or quantitative analysis of the end of procedure angiogram.

Major Adverse Event (MAE): For the purposes of this study, the definition of Major Adverse Event(s) includes:

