Rutherford Clinical Category Scale: Clinical scale identifying three grades of claudication and three grades of critical limb ischemia ranging from rest pain alone to minor and major tissue loss. (ACC/AHA PAD Practice Guidelines – Hirsch et al. 2005)

	No.: CP 64007	REV. D
	TITLE: Disrupt PAD+ Study	
	CLASS: CLINICAL PROTOCOL	PAGE 49 OF 57

Grade	Category	Clinical Description
	0	Asymptomatic
I	1	Mild claudication
	2	Moderate claudication
	3	Severe claudication
II	4	Ischemic rest pain
	5	Minor tissue loss
III	6	Ulceration or gangrene

Septicemia: One positive blood culture AND clinical evidence for infection (e.g., fever, elevated WBC count, hypotension, need for increased inotropic support, end organ dysfunction, coagulopathy/ DIC [disseminated intravascular coagulation], need for increased ventilator support, etc.).

Serious Adverse Device Effect (SADE): A serious adverse device effect is defined as an adverse device effect that results in any of the consequences characteristic of a serious adverse event or that might have led to any of these consequences if suitable action had not been taken, intervention had not been made, or if circumstances had been less opportune.

Serious Adverse Event (SAE): A serious adverse event (SAE) is defined an adverse event that:

- led to death,
- led to a serious deterioration in the health of the subject, that either resulted in:
 - a life-threatening illness or injury, or
 - resulted in a permanent impairment of a body structure or a body function, or
 - required in-patient hospitalization or prolongation of existing hospitalization, or
 - resulted in medical or surgical intervention to prevent life-threatening illness or injury or permanent impairment to body structure or a body function, or,
 - led to fetal distress, fetal death or a congenital abnormality or birth defect.

Note: Planned hospitalization for a pre-existing condition, or a procedure required by the investigational plan without serious deterioration in health, is not considered a serious adverse event.

Stroke: any neurological deficit lasting 24 hours or longer, or lasting less than 24 hours with a brain imaging study showing infarction consistent with deficit. May be further categorized as:

- Ischemic Stroke: neurologic deficit meeting the study definition for Stroke that is attributed to thromboembolic event.

	No.: CP 64007	REV. D
	TITLE: Disrupt PAD+ Study	
	CLASS: CLINICAL PROTOCOL	PAGE 50 OF 57

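### In Section 15.1, 'Infection, sepsis' fits any treated infection and 'Bacteremia' excludes a case that clears on re-culture; both are wrong as written, but only adverse-event labels are affected

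*Combined protocol and SAP*

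**What the plan says.** Section 15.1 of the protocol has six entries that bear on infection:

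- **Infection, sepsis:** "Culture-proven infections or presumptive treatment with antibiotics for clinically diagnosed infection".
- **Access Site Infection:** "Culture-proven wound infection or presumptive treatment with antibiotics for clinically diagnosed wound infection".
- **Infection, access site:** "Infection at the vascular access site, documented by lab culture or clinical evidence requiring medical treatment".
- **Infection, systemic:** "Systemic infection documented by positive lab culture or clinical evidence, requiring medical treatment to treat and resolve".
- **Septicemia:** "One positive blood culture AND clinical evidence for infection".
- **Bacteremia:** viable bacteria in the blood, with the rider "Must be confirmed by having one positive blood culture and no subsequent negative cultures".

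No rule says which entry takes precedence when an event fits several. Section 10.4.1 collects all adverse events from enrollment to 12 months, and Section 10.0 asks sites to report the diagnosis. Section 12.0 makes the sponsor responsible for classifying events. Section 13.1 lets the Clinical Events Committee set criteria for selected events in a charter that is not among these documents.

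**The concern.** The name 'sepsis' denotes a severe systemic condition, but the entry asks for less than either 'Infection, systemic' or 'Septicemia'. Apart from a plural, it is the 'Access Site Infection' sentence with the restriction to wounds removed, which suggests a drafting slip and not a chosen threshold.

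The 'Bacteremia' entry has the opposite fault. Whether an event counts depends on what happens afterwards: whether anyone took another culture, and whether treatment had worked by then.

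What is at stake is how infection events are described. Rutherford 5 subjects, who have minor tissue loss, are eligible. Active infection needing antibiotics is an exclusion, so an infection seen in follow-up will generally be a new event. Section 12.9 says the data will be used for publication, regulatory submissions and marketing. In those settings a sepsis line made up of local infections, or a bacteremia line without its treated cases, would mislead.

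**Working it through.** **Step 1. Apply the entries to five hypothetical events.**

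| Event | Infection, sepsis | Infection, systemic | Septicemia | Bacteremia |
|---|---|---|---|---|
| A. Local access-site wound infection, antibiotics given, no systemic signs | Met | Not met | Not met | Not met |
| B. Positive blood culture with fever, treated, repeat culture negative | Met | Can be met | Met | **Not met** |
| C. As B, but no repeat culture taken | Met | Can be met | Met | Met |
| D. As B, but repeat cultures stay positive | Met | Can be met | Met | Met |
| E. Culture-negative systemic illness, diagnosed clinically and given antibiotics | Met | Met | Not met | Not met |

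Three results follow.

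- Row A: a local infection with no systemic illness meets the sepsis entry.
- Rows B and C: the same bloodstream event does or does not count as bacteremia according to whether a later culture was taken and was negative. The entry sets no time limit on later cultures.
- Row E: 'Septicemia' misses culture-negative systemic illness, but 'Infection, systemic' accepts clinical evidence and captures it. This matters for the fix.

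**Step 2. Size.** The plan states no figure for infection, so there is none to reproduce. As a check on method, its one precision figure (Section 9.2: 65% of 40 lesions, 26/40) gives a Clopper-Pearson 95% interval of 48.3% to 79.4%, as stated there.

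- Input: up to 40 subjects (Section 9.2).
- Effect of one relabelled subject: 1/40 = 2.5 percentage points. With fewer subjects it is larger, for example 1/30 = 3.3 points.
- Illustration (assumed, not in the documents): if 4 of 40 subjects have a treated infection and all are labelled sepsis, the rate reads 4/40 = 10% (exact 95% interval 2.8% to 23.7%), possibly with no systemic illness at all. A range of 2 to 8 subjects gives 5% to 20%.

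**Step 3. Chance that it matters at all.** For an assumed per-subject risk p of an affected event, the chance of at least one among 40 is 1 − (1 − p)^40.

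| Assumed p | Chance of at least one |
|---|---|
| 0.5% | 18% |
| 1% | 33% |
| 2% | 55% |
| 5% | 87% |
| 10% | 98.5% |

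**The case against.** A reader might infer that the trial's sepsis and bacteremia counts will be wrong, or that serious infection will be under-counted. The documents do not support either inference.

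- Neither term is an endpoint or a component of the major adverse event definition, and Section 9 plans no table of sepsis or bacteremia.
- Section 10.0 asks for a diagnosis, and local or chest infections have more specific entries, including 'Access Site Infection' and 'Pneumonia'. Overlap in wording does not show that sites would choose 'sepsis'. The 10% illustration is therefore the literal worst case for its assumed four events.
- Seriousness follows the criteria in Section 10.1.2, not the infection label. A cleared bacteremia is still collected. It meets 'Septicemia' if there is clinical evidence, and it can meet 'Infection, systemic'.
- The Clinical Events Committee charter may set its own criteria.

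All of this stands, and it limits the consequence to labels. It does not rescue the wording, because nothing in the documents says that 15.1 is overridden.

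The bacteremia condition could also be read as a guard against contaminated cultures. It serves that purpose poorly. A single positive that is never repeated passes, while a true case cleared by treatment fails.

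**Conclusion.** The point holds as a minor error of definition. Followed literally, 'Infection, sepsis' takes in any culture-proven or antibiotic-treated infection, and 'Bacteremia' drops a true case once a later culture is negative. Both conflict with 'Septicemia', and neither is reconciled with 'Infection, systemic'.

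The effect is confined to adverse-event category labels, at 2.5 percentage points per affected subject if 40 are enrolled. It arises only if such events occur and only if 15.1 is used as the coding rule. The bacteremia half also needs a repeat culture to have been taken and to be negative. The primary safety endpoint, the performance endpoint, serious adverse event status and total adverse events do not change.

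**What to change.** Make two edits in Section 15.1.

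1. Delete 'Infection, sepsis' and classify such events under the existing 'Septicemia' or 'Infection, systemic' entries; purely local infections stay under their own entries. Deleting is better than copying the 'Septicemia' criteria into the sepsis entry, because those criteria require a positive blood culture and would leave culture-negative sepsis outside the entry.
2. In 'Bacteremia', remove the condition on later cultures, so that clearance on treatment does not cancel an event. Leave suspected contaminants to adjudication.

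Then recheck infection events already coded, and confirm that the Clinical Events Committee charter agrees with the revised entries if it covers infection.

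The cost is two wording changes and one review of coded events, with no new data collection. The small downside is that a few contaminant cultures may need individual review.

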15.2 List of Abbreviations

ABI	Ankle-brachial Index
ADE	Adverse Device Effect
AE	Adverse Event
ASADE	Anticipated Serious Adverse Device Effect
CEC	Clinical Events Committee
CRF	Case Report Form
CRO	Contract Research Organization
DUS	Duplex Ultrasound
EDC	Electronic Data Capture
EC	Ethics Committee
FDA	Food and Drug Administration
ICF	Informed Consent Form
IFU	Instructions for Use
IRB	Institutional Review Board
ITT	Intent-to-Treat
IVL	Intravascular Lithotripsy
MAE	Major Adverse Event
OTW	Over the Wire
PAD	Peripheral Artery Disease
RC	Rutherford Category
SADE	Serious Adverse Device Effect
SAE	Serious Adverse Event
TLR	Target Lesion Revascularization
TVR	Target Vessel Revascularization
UADE	Unanticipated Adverse Device Effect
USADE	Unanticipated Serious Adverse Device Effect

	No.: CP 64007	REV. D
	TITLE: Disrupt PAD+ Study	
	CLASS: CLINICAL PROTOCOL	PAGE 52 OF 57

17.0 SUBJECT INFORMED CONSENT

The subject informed consent template will be provided as a separate attachment.

	No.: CP 64007	REV. D
	TITLE: Disrupt PAD+ Study	
	CLASS: CLINICAL PROTOCOL	PAGE 55 OF 57

18.0 CASE REPORT FORMS

Draft case report forms will be provided as a separate attachment.

	No.: CP 64007	REV. D
	TITLE: Disrupt PAD+ Study	
	CLASS: CLINICAL PROTOCOL	PAGE 56 OF 57

19.0 REVISION HISTORY

Revision	Release Date	DCO #	Reason(s) for Revision	Doc Owner
A	9/30/2020	21051	Initial release.	Clinical
B	10/7/2020	21069	Added longer catheter working length to the study rationale; revised angiographic inclusion criteria #8 to reflect vessel diameter for common iliac; added option for intravascular imaging to schedule of events and procedural discussion; administrative changes.	Clinical
C	10/19/2020	21128	Updated Index Procedure section with additional sizing recommendation and revised sequence chart based on current IFU; corrected visit label in Schedule of Events; added explanatory language in Data Management section to be in compliance with NZ National Ethical Standards; removed DSMB reference as not applicable, administrative changes.	Clinical

	No.: CP 64007	REV. D
	TITLE: Disrupt PAD+ Study	
	CLASS: CLINICAL PROTOCOL	PAGE 57 OF 57

Revision	Release Date	DCO #	Reason(s) for Revision	Doc Owner
D	4/27/2021	21704	
 Updated study objective to indicate that the study is being conducted in the US to evaluate continued safety and effectiveness in a postmarket setting with a cleared medical device. Updated to include US centers following FDA clearance of the M5+ catheter. Clarified use of devices allowed for treatment of non-target lesion(s). Added additional explanatory text for sample size determination. Clarified MDR reporting requirements pertaining to serious adverse events. 	Clinical
